SYNOPSIS APPAHOCA study

Feasibility of adapted physical activity based on a walking platform for elderly patients hospitalized for cancer

ID-RCB: 2018-A00031-54

Version n°2.1 07/10/2018

SPONSOR	Centre François Baclesse [name]
----------------	---

COORDINATING INVESTIGATORS	[name] [name] CHU - [name] [name] [name] Centre François Baclesse [name]
-----------------------------------	---

REGULATORY APPROVALS	CPP IDF 5	Date: 06/03/2018
-----------------------------	-----------	------------------

TITLE	Feasibility of adapted physical activity based on a walking platform for elderly patients hospitalized for cancer
ACRONYM	APPAHOCA
Coordinator	[name] [name]
Indication	Elderly patients hospitalized for cancer
Test methodology	Multicenter, prospective, non-randomized, open-label pilot feasibility study
Objectives	
Main objective
 
Assess the feasibility of adapted physical activity (APA) based on a walking platform in patients aged 70 and over hospitalized for cancer.
 
Secondary objectives
 
 ▪ Describe adherence to adapted physical activity, in quantitative and qualitative terms ▪ Investigate factors associated with adherence: oncological factors, social factors, previous mobility, cognitive level, comorbidities ▪ Assess patient satisfaction with using an adapted walking platform
Judgment criteria	
Main criteria
 
 ▪ Percentage of patients included who complete at least two sessions of 6 minutes or more of adapted physical activity on the walking platform. Adapted physical activity on a walking platform will be considered feasible if $\geq 70\%$ of patients complete ≥ 2 sessions of 6 minutes or more during their hospitalization for cancer lasting ≥ 48 hours. 
Secondary criteria
 
Patient adherence to adapted physical activity will be assessed:
 
 • Quantitatively (intensity of participation): number and duration of sessions, number and regularity of steps, maximum and average walking speed, distance covered • Qualitatively: 
 ◦ Reason for not completing the first and/or second session, ◦ Type of activity: use of balance games, chosen visual walking route 
Factors that may be associated with adherence:
 
 • Gender, age, socio-professional category before retirement • Location of cancer, reasons for hospitalization (medical or surgical) • Pain • Activity before hospitalization: Performance Status, previous QAPPA activity level, history of falls in the past year • Cognitive status prior to the first session: memory test (temporal-spatial orientation/10, learning and recalling 3 words) • Activity prior to the first session: Ability to walk 4 meters (alone/with technical and/or human assistance) and time required; Ability to transfer (alone/with technical and/or human assistance); Physical therapy already underway • Context, presence of severe comorbidity(ies) affecting mobility, presence of isolation due to multi-resistant bacteria, presence of medical equipment (IV, drain, urinary catheter, enteral feeding tube, ostomy bag, oxygen therapy glasses) 
Patient satisfaction with the use of the adapted walking platform will be assessed at each session on a scale of 0 to 10 on the following items:
 
 • Fear of falling

	
 • Use of the treadmill • Satisfaction with the digital tablet on the walking platform • Instructional support from the APA educator (starting from the second session)
Inclusion criteria	
 - Patients with cancer - Patients over the age of 70 hospitalized for 48 hours or more - Patients identified as eligible for a medical prescription for APA - Proficiency in French - Patients affiliated with a social security system - Patients who have given their written consent
Exclusion criteria	
 - Patients who are completely unable to communicate - Patients receiving palliative care in the terminal phase - Patients who are less than 1.35 m or more than 2 m tall and/or weigh more than 130 kg - Patients who are unable to participate in APA sessions - Patients who are unable to wear a support harness - Patients deprived of their liberty or under guardianship - Patients unable to comply with the requirements of the protocol for geographical, social, or psychopathological reasons
Description of the protocol/experimental design	
After checking the patient's ability to participate in walking sessions and obtaining a medical prescription, the physical activity instructor will ask patients questions about their usual activities prior to hospitalization.
 
During the patient's hospitalization, physical activity on the adapted ema® walking platform will be offered every working day, in the form of a session lasting a minimum of 6 minutes and a maximum of 30 minutes.
 
The walking sessions will be carried out on an adapted walking platform, comprising a treadmill and a connected tablet. The tablet allows patients to view a landscape or play balance or memory games while walking. The activity offered will be tailored to the patient's profile.
 
Patients will be brought to the platform in a wheelchair and returned to their room by the same means of transport.
 
At the end of each session, patients will complete a satisfaction questionnaire.

Number of subjects	To estimate a proportion of 70% of patients with a 95% confidence interval of [45-95], it is necessary to include 50 evaluable patients. To anticipate potential non-evaluable patients, we plan to include 60 patients.
Participating centers	2
Study duration	6 months

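### Session count is an adherence measure with no denominator, although offers accrue over a stay of open length, so factor associations may be confounded by length of stay

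*Protocol*

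**What the plan says.** All references are to the protocol synopsis.

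- **Secondary objectives:** "Investigate factors associated with adherence: oncological factors, social factors, previous mobility, cognitive level, comorbidities".
- **Judgment criteria, secondary criteria:** adherence is assessed "Quantitatively (intensity of participation): number and duration of sessions, number and regularity of steps, maximum and average walking speed, distance covered". None of these is expressed per session offered or per day of stay. The qualitative part includes "Reason for not completing the first and/or second session", so non-participation is described for two sessions only.
- **Judgment criteria, factors that may be associated with adherence:** a detailed list covering demographics, cancer site, medical or surgical admission, pain, prior activity, cognition, mobility, comorbidity, isolation and medical equipment. Length of stay and number of sessions offered are not on it.
- **Inclusion criteria:** "Patients over the age of 70 hospitalized for 48 hours or more". No upper limit and no common observation window is given.
- **Description of the protocol/experimental design:** activity "will be offered every working day, in the form of a session lasting a minimum of 6 minutes and a maximum of 30 minutes".
- **Main criterion:** "Percentage of patients included who complete at least two sessions of 6 minutes or more". This binary is also not related to the number of sessions offered.

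**The concern.** With one offer per working day, a patient cannot complete more sessions than there are working days in the stay. Two patients who accept offers equally readily will have different counts if one stays longer. Several listed factors could plausibly differ in stay, for example medical versus surgical admission, cancer site, severe comorbidity, isolation or drains.

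Three errors are then possible in the factor analysis:

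- a factor unrelated to willingness to take part appears associated with adherence;
- a real difference in uptake is hidden because the less willing group stays longer;
- a real difference appears in the wrong direction.

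Steps, duration and distance share the problem if they are summed over the stay, which the text does not say. Walking speed and step regularity do not accumulate and are not affected.

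**Working it through.** The protocol states no figure on this point, so there is none to reproduce. The check has an exact part and a simulated part, and both rest on assumed stays and uptake.

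**1. Expected count.** If a patient is offered *d* sessions and accepts each with probability *p*, the expected count is *d·p*. At *p* = 0.7 this is 1.4 for 2 offers, 2.1 for 3, 3.5 for 5 and 7.0 for 10. Uptake is identical throughout and only the stay differs.

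**2. At least two sessions, fixed number of offers.** P(≥2) = 1 − (1−p)^d − d·p·(1−p)^(d−1). At *p* = 0.6:

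| Offers | P(≥2) |
|---|---|
| 2 | 1 − 0.16 − 0.48 = 0.36 |
| 3 | 1 − 0.064 − 0.288 = 0.65 |
| 4 | 1 − 0.0256 − 0.1536 = 0.82 |
| 6 | 1 − 0.0041 − 0.0369 = 0.96 |

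**3. Simulation inputs.** The design is 25 vs 25 patients (the 50 evaluable patients of the sample-size statement, split equally by assumption). Working days are 1 + Poisson(mean − 1), and sessions are Binomial(days, p). Uptake has mean 0.6 in both groups, either fixed or varying between patients as Beta(6,4), Beta(3,2) or Beta(1.5,1). There are 4,000 trials per scenario and tests are at 5%. Since true uptake is equal, every rejection is false as a statement about uptake.

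Ranges run over the four uptake distributions, using the Mann-Whitney test:

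| Mean working days | Raw count rejected | Completed/offered rejected |
|---|---|---|
| 4 vs 4 | 5% | 4–6% |
| 4 vs 5 | 17–25% | 4–6% |
| 4 vs 6 | 46–71% | 4–6% |
| 3 vs 5 | 59–81% | 4–6% |

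The raw-count rate falls as between-patient variation in uptake grows.

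**4. Two-session outcome, 4 vs 6 days.** With fixed uptake and days = 1 + Poisson(λ), P(≥2) = 1 − e^(−λp)·[1 + (1−p)·λp].

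- λ = 3: 1 − e^(−1.8) × 1.72 = 0.716
- λ = 5: 1 − e^(−3) × 2.20 = 0.890

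With the widest variation in uptake the proportions are 65% vs 79%. Fisher's test rejects in 12–24% of trials, against 2.0–2.6% when stays are equal.

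**5. Masking and reversal.** Uptake is Beta with precision 5. The higher-uptake group stays 4 days and the lower-uptake group 6.

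- *Masking*, uptake 0.75 vs 0.50: expected counts are 4 × 0.75 = 3.0 and 6 × 0.50 = 3.0. The true difference is detected in the correct direction in 3.5% of trials by raw count and 86% by completed/offered.
- *Reversal*, uptake 0.65 vs 0.55: expected counts are 2.6 and 3.3. The raw count is significant in the wrong direction in 21% of trials, the ratio in 0.1%.

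**6. Other assumptions.** With fixed uptake of 0.5 to 0.7 and a pooled two-proportion test for the ratio, the raw count is rejected in 35–56% of trials for mean offers 2 vs 3 and 69–88% for 3 vs 5. The ratio stays at about 4–6%.

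**The case against.** The strongest reply is that the quoted line lists measures and is not an analysis rule. It serves the descriptive adherence objective, for which raw counts are legitimate. The protocol does not say which adherence variable enters the factor analysis, and an SAP could add an offset for working days without contradicting it. It follows that the raw count cannot be assumed to be the analysed outcome, and this is why the two-session binary was also examined. The reply does not remove the point: the protocol itself defines quantitative adherence as an unindexed number and sets out a long factor list without stay.

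A second reply is that the two-session outcome is less affected: about 6–8% false rejection at 4 vs 5 days. That is true, although Fisher's test rejects only about 2% when stays are equal, so it is still a rise.

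Third, the magnitudes are all assumed. The masking case is chosen so that the means cancel, and the wrong-direction rate drops from 21% to between 3% and 4% if stays are 4 vs 5 days. At 4 vs 4.5 days with equal uptake the raw count is rejected in about 9%. These limits stand, and the figures are illustrations only.

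Fourth, the denominator may be derivable from stay dates, and a synopsis need not list every recorded item. That is fair, and it makes the remedy cheaper.

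Finally, total sessions and uptake per offer are different estimands. That is also true, and it is why the recommendation keeps raw counts as description and asks for associations with and without adjustment.

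**Conclusion.** The concern holds. As written, the number of sessions mixes opportunity with uptake, and associations between listed factors and that count, or with reaching two sessions, may be confounded by length of stay. The distortion is conditional: there is none for a factor whose groups have similar stays. Its actual size cannot be computed from the protocol. Under the assumptions shown, false rejection for the raw count runs from 5% with equal stays, through 17–25% at 4 vs 5 working days, to 46–71% at 4 vs 6; for the two-session outcome at 4 vs 6 it is 12–24%.

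The point affects an exploratory secondary objective of a pilot study and does not touch the 70% feasibility rule. It should be corrected because the factor results would otherwise be hard to interpret and the correction is cheap. Confidence is medium, because the outcome of the factor analysis is not stated and stays and uptake are unknown.

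**What to change.** 1. Record for each patient the number of sessions offered, or the inclusion and discharge dates from which available working days can be counted.
2. For the factor analysis, define session adherence as sessions completed divided by sessions offered. Analyse it with a binomial model that allows for between-patient variation, such as beta-binomial or quasi-binomial.
3. Where the outcome is at least two sessions, show each association with and without adjustment for sessions offered, since a factor may act partly through stay.
4. Report steps, distance and duration per session. Keep raw counts as descriptive measures. Speed and step regularity need no change.

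The cost is one extra item per patient, which the document does not list and which may already be derivable from stay dates, plus one or two lines of wording. No extra patients or visits are needed.

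### Do the inclusion criteria describe a different population from the one the objective and the feasibility rule refer to?

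*Protocol*

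**What the plan says.** The title and the Indication field of the protocol describe the population as "elderly patients hospitalized for cancer" (the Indication field with a capital E). The main objective, under Objectives, is to assess feasibility "in patients aged 70 and over hospitalized for cancer".

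Under Judgment criteria, the main criterion is the "Percentage of patients included who complete at least two sessions of 6 minutes or more". A second sentence gives the decision rule: the activity is feasible if at least 70% of patients reach two such sessions "during their hospitalization for cancer lasting ≥ 48 hours". Neither sentence states an age.

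The Inclusion criteria have six items. The two that matter here are "Patients with cancer" and "Patients over the age of 70 hospitalized for 48 hours or more". No item says that cancer must be the reason for the stay, and none of the seven Exclusion criteria removes unrelated admissions. The only planned variable on the reason for admission, among the factors possibly associated with adherence, separates medical from surgical stays.

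**The concern.** Eligibility lists are what sites apply at the bedside, and here the list does not repeat the objective. Two mismatches appear.

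- **Age.** The objective starts at 70. The list, taken literally, starts above 70. Two centres could screen the same 70-year-old differently.
- **Reason for admission.** Having cancer and being in hospital for at least 48 hours are separate conditions in the list. A patient with cancer admitted for something else meets both. That patient joins the denominator, which is everyone included, while the decision rule speaks of a cancer admission. It could then be unclear whether that patient's completed sessions count as a success.

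The second mismatch is the weightier one because it touches the primary endpoint. If the numerator and denominator were drawn from different groups, the comparison with 70% would be biased against feasibility. If they were not, the verdict would still cover some patients outside the stated target population.

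**Working it through.** The protocol attaches no figure to this point, so there is nothing to reproduce. The check compares the wordings and then bounds the possible effect.

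**Age.** The objective requires age ≥ 70. The inclusion item can be read in two ways:

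- past the 70th birthday, which agrees with the objective in all but the birthday itself;
- age in completed years above 70, which leaves out patients who are 70.

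On either reading every enrolled patient satisfies the objective's limit. The enrolled group is a subset of the target, so nobody outside the age range enters the percentage. The main criterion states no age, so the age mismatch is with the objective only.

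**Reason for admission.** The places that bear on it are:

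| Place in the protocol | Link between cancer and the stay |
|---|---|
| Title, Indication | stay is for cancer |
| Main objective | stay is for cancer |
| Main criterion, defining sentence | none; all included patients |
| Main criterion, decision rule | stay is for cancer |
| Inclusion criteria | cancer present; link not repeated |
| Description of the protocol | none; sessions offered throughout the stay |

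Four elements (title, indication, objective, decision rule) state the link. The others are silent, and none states the opposite. In the defining sentence, numerator and denominator both come from included patients. In the decision rule, "during their hospitalization for cancer lasting" reads most naturally as a description of the stay those patients are having, not as a condition that cancels sessions they completed.

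**Bounding the effect.** Inputs: 60 planned inclusions (Number of subjects), the 70% threshold (Main criteria), and *k*, the number of unrelated admissions among the 60. The protocol gives no value for *k*, so those used here are assumptions.

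Successes needed: 0.70 × 60 = 42.

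*Reading A: unrelated admissions stay in the denominator but can never succeed (worst case).* The rate needed among the other patients is 42/(60 − k):

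- k = 1: 42/59 = 71.2%, a shift of 1.2 points
- k = 3: 42/57 = 73.7%, a shift of 3.7 points
- k = 6: 42/54 = 77.8%, a shift of 7.8 points

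*Reading B: their sessions count like anyone else's, as in the defining sentence.* The threshold stays at 42/60 = 70%. The observed percentage moves by k/60 of the difference in success rate between the two groups. For k = 3 that is 3/60 = 5% of the difference.

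*Reading C: the analyst restricts the percentage to cancer admissions.* The threshold stays at 70% of 60 − k patients. Only precision changes.

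Standard error at 70%:

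- n = 60: √(0.7 × 0.3/60) = 5.9 points
- n = 57: √(0.7 × 0.3/57) = 6.1 points
- n = 54: √(0.7 × 0.3/54) = 6.2 points

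The threshold moves only under Reading A. For k = 1 to 3 the shift is below one standard error. For k = 6 it exceeds one, but that needs 10% unrelated admissions, all scored as failures whatever they did.

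**The case for a change.** The strongest argument for acting is that a title or an indication is not an eligibility criterion. A site that follows the list can properly enrol a patient with cancer who was admitted for another condition. The protocol expects severe comorbidities that affect mobility, and a university hospital (CHU) appears beside the cancer centre among the coordinating investigators' affiliations, so such admissions are conceivable. The correction would be two phrases with no extra patients, and a later analysis rule cannot repair an eligibility list.

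Part of this stands. The wordings do differ, the list does not exclude unrelated admissions, and the medical or surgical variable would not identify them afterwards. It is also true that aligning the phrases would cost almost nothing.

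The step from wording to consequence does not stand. That the university hospital would contribute unrelated admissions is an inference; the protocol nowhere says so. The document is a synopsis, where a criterion can be shortened because the indication above it has already named the population. The supposed clash between denominator and success definition arises only if a descriptive phrase in the decision rule is treated as a scoring rule that overrides the sentence defining the endpoint. Low cost alone is not a reason to change a plan when no result can be shown to depend on the change.

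**Conclusion.** The concern is right about the text but does not call for a change. The age difference is loose wording: it affects at most patients aged exactly 70 and admits nobody outside the objective's range. The admission difference is an unrepeated phrase, and four other elements of the synopsis settle the intended population. An analyst who follows the endpoint sentence as written counts every included patient in both numerator and denominator and compares the result with an unchanged 70%.

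No effect on the verdict can be computed, because the protocol gives neither the share of unrelated admissions nor the share of patients aged exactly 70. Under the least natural scoring rule, 1 to 3 unrelated admissions among 60 would raise the bar by 1.2 to 3.7 points, against a standard error of 5.9 points.

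This conclusion rests on two assumptions: that sites read the inclusion list together with the indication, so unrelated admissions are few or absent, and that completed sessions are counted for every included patient. If a substantial share of unrelated admissions were deliberately enrolled, the feasibility claim would describe a broader group than the objective names. Nothing in the protocol points to that intention.

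### The minimum stay is set in clock hours but sessions run once per working day, so some eligible weekend stays cannot meet the two-session primary criterion

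*Protocol*

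**What the plan says.** Four statements in the protocol synopsis bear on this.

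- **Inclusion criteria:** "Patients over the age of 70 hospitalized for 48 hours or more". The limit is in clock hours, with no reference to working days.
- **Judgment criteria, main criterion (outcome and denominator):** "Percentage of patients included who complete at least two sessions of 6 minutes or more of adapted physical activity on the walking platform". The denominator is everyone included.
- **Judgment criteria, main criterion (success rule):** the activity is judged feasible if at least 70% of patients reach that level "during their hospitalization for cancer lasting ≥ 48 hours". Both sessions must therefore fall within the stay.
- **Description of the protocol/experimental design:** platform activity "will be offered every working day, in the form of a session lasting a minimum of 6 minutes and a maximum of 30 minutes". Read naturally, this means one session per working day and none at weekends. A check of the patient's ability and a medical prescription come first; how long they take is not stated.

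The secondary criteria also record "Reason for not completing the first and/or second session". Nothing in the document removes a patient whose stay held fewer than two working days.

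**The concern.** The protocol already sets a minimum stay, so it intends to screen out stays that are too short for the outcome. It does so in a unit that does not match its session schedule. Two sessions at one per working day need two working days, and 48 hours does not guarantee them. For a patient admitted just before or during a weekend for 48 hours, the primary outcome is fixed before any session is offered.

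What is at stake is how the pass/fail verdict is read. A failure that is certain from the admission date says nothing about whether an elderly inpatient can or will use the platform, yet it carries the same weight as a refusal or a physical inability. All such cases push the observed percentage the same way, downward.

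**Working it through.** **Inputs.** From the protocol: minimum stay 48 hours; one session per working day; success at two or more sessions; denominator all included patients; threshold 70%; 60 planned inclusions. Assumed: working days are Monday to Friday with no public holiday; completion probabilities of 75%, 80% and 85% among patients with two opportunities; 0 to 6 affected patients. The protocol gives no figure of its own on this point to reproduce.

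**Step 1: working days touched by a stay, best case.** Assume no start-up delay and that both the admission day and the discharge day can be used.

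| Admission day | Mon | Tue | Wed | Thu | Fri | Sat | Sun |
|---|---|---|---|---|---|---|---|
| 48-hour stay | 3 | 3 | 3 | 2 | 1 | 1 | 2 |
| 72-hour stay | 4 | 4 | 3 | 2 | 2 | 2 | 3 |

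At exactly 48 hours, Friday and Saturday admissions fall short of two; at 72 hours none does. The Friday case needs no assumption about session hours. The Saturday case matters only if the patient is included over the weekend or on the Monday of discharge, and the document does not describe that timing.

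**Step 2: sensitivity to session hours and delay.** Suppose sessions run only from 09:00 to 17:00 and admissions are spread evenly over all hours of the week. The share of admission hours that leaves fewer than two opportunities is then:

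| Stay | No delay | 12-hour delay | 24-hour delay |
|---|---|---|---|
| 48 h | 39% | 55% | 83% |
| 72 h | 20% | 31% | 39% |
| 96 h | 0% | 6% | 20% |
| 120 h | 0% | 0% | 0% |

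These are shares at fixed stay lengths under assumed hours. They are not estimates of the share of trial patients.

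**Step 3: what the remaining patients must achieve.** The threshold is 0.70 × 60 = 42 completers. If k patients cannot succeed, the required completion among the others is 42/(60 − k):

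- k = 1: 42/59 = 71.2%
- k = 2: 42/58 = 72.4%
- k = 3: 42/57 = 73.7%
- k = 6: 42/54 = 77.8%

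**Step 4: chance of reaching 42 completers.** P(X ≥ 42) with X binomial(60 − k, p), where p is the assumed completion among patients with two opportunities:

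| p | k = 0 | k = 1 | k = 2 | k = 3 | k = 6 |
|---|---|---|---|---|---|
| 75% | 85.1% | 79.8% | 73.3% | 65.7% | 38.6% |
| 80% | 97.8% | 96.4% | 94.2% | 90.9% | 72.6% |
| 85% | 99.9% | 99.8% | 99.6% | 99.2% | 94.7% |

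The effect is small with one or two affected patients and completion of 80% or more. It becomes material only if several patients are affected or if true completion lies close to the threshold.

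**The case against.** The strongest reply is that this is a choice of what feasibility means. In a pilot study, whether a weekday service fits real hospital stays can be part of the question, and a weekend stay that ends before a second session is then a result rather than a bias. The recorded reasons for non-completion would let such cases be identified. Part of this stands: logistics belong in a feasibility outcome, which is why unexpected early discharges should go on counting as non-completers. But the protocol has already chosen to set a minimum stay, and only its unit fails to match the schedule. Recording reasons explains the failures afterwards without changing the verdict.

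A second reply is that materiality is not shown. That stands. There are no length-of-stay data, and nothing in the document supports six affected patients over one or none. Two of seven admission weekdays is not a share of patients.

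Other wordings offer no clear escape. If the limit means 48 hours already spent in hospital at inclusion, no remaining stay is guaranteed. If more than one session a day were allowed, the text does not say so.

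A reader might also infer that the sample-size statement contradicts the main criterion, because it says "it is necessary to include 50 evaluable patients" and then "To anticipate potential non-evaluable patients, we plan to include 60 patients", while the criterion counts everyone included. The document does not support that inference. Non-evaluable patients could be consent withdrawals, ineligible inclusions or patients with missing session data, and the definition may stand in an analysis plan that is not shown.

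**Conclusion.** The mismatch is real on the document's own wording. A 48-hour Friday-to-Sunday stay satisfies the inclusion criterion, offers at most one session, and is scored as a failure; a Saturday-to-Monday stay is scored the same way if the patient is included. The direction of the effect is known (downward), but its size is not. It is confined to short stays: in the best case it is gone at 72 hours, and even with a 24-hour delay and the assumed session hours it is gone at 120 hours.

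A reader might go further and conclude that the 70% verdict is likely to be wrong, or that completion must be very high to pass. The document supports neither. The 73% chance at 80% completion requires six of 60 patients to be affected, and at 85% completion the chance is still 94.7% with six. This is a minor design point, worth correcting because the correction is cheap.

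**What to change.** In the inclusion criterion and again in the main criterion, replace the clock-hour condition with an expected stay that contains at least two working days on which a session can be offered, counted from inclusion. State whether the day of inclusion counts. Leave the session schedule as it is.

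Keep all included patients as the primary denominator, with unexpected early discharges counted as non-completers. Completion among patients who were offered at least two sessions can be reported as supplementary only, because that subgroup is defined by events after inclusion.

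The cost is one phrase in two places and three modest drawbacks. Eligibility comes to rest on a predicted stay, which staff may judge differently. The feasibility claim covers slightly longer stays than it does now. The pool for 60 inclusions at two centers in 6 months becomes slightly smaller. A patient with exactly two opportunities still has no margin for a missed session, so the change removes only failures that are certain from the calendar.

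### The 95% confidence interval of 45 to 95 does not belong to 50 patients: 50 give about 57 to 83, and 45 to 95 needs only about 13

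*Protocol*

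**What the plan says.** The Number of subjects entry of the protocol synopsis frames the size as an estimation problem: "To estimate a proportion of 70% of patients with a 95% confidence interval of [45-95], it is necessary to include 50 evaluable patients". It then adds a margin: "To anticipate potential non-evaluable patients, we plan to include 60 patients". It gives no null hypothesis, test, power or non-evaluable rate.

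The entry Judgment criteria, Main criteria, sets out the quantity being estimated: "Percentage of patients included who complete at least two sessions of 6 minutes or more of adapted physical activity on the walking platform". The same entry gives the decision rule, which begins "Adapted physical activity on a walking platform will be considered feasible if" and sets the bar at an observed 70% or more. The planning proportion and the feasibility threshold are thus the same value.

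**The concern.** The interval 45 to 95 is exactly symmetric about 70, so it reads as a deliberate margin of plus or minus 25 points. That is very wide for 50 patients, and it suggests that the interval and the number did not come from the same calculation.

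Two things are at stake. First, this sentence is the only sample-size justification in the document, and it calls 50 patients necessary for a precision that far fewer would deliver. Second, it is the only statement of precision near the 70% feasibility rule. A reader who takes it at face value will think that a result just meeting the rule is compatible with a true completion rate of 45%, a minority of patients. The data would in fact put the lower 95% limit in the mid-50s, a majority.

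**Working it through.** **Inputs**, all from the protocol synopsis:
- proportion p = 0.70, so p(1 − p) = 0.21
- two-sided 95% confidence, z = 1.96
- printed interval 0.45 to 0.95, so half-width d = 0.25
- 50 evaluable patients, 60 included

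**Step 1: attempt to reproduce the stated 50.** The precision formula for a single proportion is n = z² p(1 − p) / d².
- d = 0.25: 1.96² × 0.21 / 0.0625 = 12.9, so 13 patients.
- Check at n = 13: 1.96 × √(0.21/13) = 0.249, giving 45.1 to 94.9. This is the printed interval.

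The stated 50 is not reproduced; 50 / 12.9 = 3.9.

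**Step 2: the interval that 50 patients give.** The half-width is 1.96 × √(0.21/50) = 0.127. For 35 of 50:

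| Method | 95% interval (%) |
|---|---|
| Normal approximation (Wald) | 57.3 to 82.7 |
| Wald with continuity correction | 56.3 to 83.7 |
| Wilson | 56.2 to 80.9 |
| Exact (Clopper-Pearson) | 55.4 to 82.1 |

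No method comes near 45 at the lower end or 95 at the upper end. The printed half-width is 25 / 12.7 = 1.97 times the actual one.

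If all 60 included patients count, the Wald half-width is 1.96 × √(0.21/60) = 0.116, giving 58.4 to 81.6. The exact interval for 42 of 60 is 56.8 to 81.2.

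**Step 3: could another method link 50 with 45 to 95?**
- Wald with continuity correction, half-width 25 points: about 17 patients.
- Exact interval, total width 50 points or less: about 15.
- Exact interval, lower limit at 45%: about 19.
- Worst case p = 0.5: 1.96² × 0.25 / 0.0625 = 15.4, so 16.
- Higher confidence: at n = 50, 25 points is 0.25 / √(0.21/50) = 3.86 standard errors, which corresponds to a 99.99% interval rather than 95%.
- A one-sample test of 45% against 70%, two-sided 5%: 30, 40 and 48 patients for 80%, 90% and 95% power. Only the last is near 50.

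**Step 4: likely source of the slip.** Taking 25 points as the total width, d = 0.125: 1.96² × 0.21 / 0.015625 = 51.6, so 52 patients. This is close to 50 and implies an intended interval of about 57.5 to 82.5.

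**The case against.** The strongest reply is that the error is on the safe side. Fifty patients give better precision than the protocol promises, so the study is not undersized for its stated aim. The feasibility rule compares the observed percentage with 70% and does not use the interval, so no verdict would change. That is correct, and it limits the harm. It does not make the sentence true, and the sentence carries the whole sample-size argument in the document.

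A second reply is that 50 might come from a test of 45% against 70%, which needs 48 patients at 95% power. The text gives no test, null value or power and speaks of estimating with a confidence interval, so this reading has no support in it.

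Three qualifications do stand:
- The figure of 13 is the Wald result. Other interval methods give about 15 to 19, still far below 50.
- The document does not say whether the interval or the 50 was intended. The near match at 52 makes the interval the likelier slip, but that is an inference.
- The lower limit of about 55 to 57% belongs to an observed 35 of 50. It moves with the result and with the denominator, which is patients included in the main criterion but evaluable patients in the sample-size sentence.

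Finally, the available text is a synopsis, and a fuller protocol might set out the calculation. That would not correct the figure printed here.

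**Conclusion.** The concern holds. No standard 95% method pairs 50 patients with an interval of 45 to 95 around 70%. The printed half-width is about twice the true one (25 against 12.7 points), and the printed number is about 3.9 times what the printed interval requires under the Wald formula. At the feasibility cut-off of 35 of 50, the lower 95% limit is 57.3% (Wald) or 55.4% (exact), not 45%.

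The finding rests on the protocol's own inputs and on treating patients as independent. It concerns the pairing of the two figures. It does not show that 50 patients are too few or too many for the study's purpose. The sentence must be corrected because it is the only basis given for the sample size.

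**What to change.** The sponsor should confirm the precision that was intended. If 50 was the intended number, as the arithmetic suggests, keep 50 evaluable and 60 included and replace the interval. Suggested wording: *With 50 evaluable patients and an observed proportion of 70%, the 95% confidence interval is 57% to 83% (exact method: 55% to 82%).* If the interval was intended instead, the justification for 50 has to be rewritten.

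Beside the 70% rule in Main criteria, it would help to add that a result of exactly 35 of 50 has an exact lower 95% limit of about 55%. If the denominator is all 60 included patients, the matching figure for 42 of 60 is about 57%.

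The cost is one corrected sentence and one short optional addition, with no change to patients, visits or procedures.
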